### **2.1.1 General definitions**

#### **2.1.1.1 Study drug and study treatment**

Study drug and study treatment both refer to Dabrafenib in Combination with Trametinib.

#### **2.1.1.2 Date of first/last administration of study drug**

The date of first administration of study drug is defined as the first date when a non-zero dose of study drug is administered and recorded on the exposure form. For the sake of simplicity, the date of first administration of study drug will also be referred as start date of study drug.

The date of last administration of study drug is defined as the last date when a non-zero dose of study drug is administered and recorded on the exposure form. This date is also referred as last date of study drug.

#### **2.1.1.3 Study day**

The study day for all assessments (e.g. tumor assessment, death, disease progression, tumor response, performance status, adverse event onset, laboratory abnormality occurrence, vital sign measurement, dose interruption) will be calculated using the start date of study drug as the origin. For assessments occurring after or on the start date of study drug, study day will be calculated as:

$$\text{Study Day} = \text{Event date} - \text{start date of study drug} + 1.$$

The first day of study drug is therefore study day 1.

For any assessment or events such as baseline disease characteristics or medical history (e.g., time since diagnosis of disease) occurring prior to the start of the study drug, study day will be negative and will be calculated as:

$$\text{Study Day} = \text{Event date} - \text{start date of study drug}.$$

The study day will be displayed in the data listings.

#### **2.1.1.4 Baseline**

Baseline will be defined as the most recent non-missing value during the screening period prior to the first dose of study treatment. For Patient Reported Outcomes (PRO), baseline date will be the same as Cycle 1 Day 1 for each participant given ePROs will be completed prior to any other assessments and treatments on Cycle 1 Day 1. For laboratory data, baseline will be

defined as the most recent non-missing value from a laboratory during the screening period prior to the first dose of study treatment. If patients have no value as defined above, the baseline results will be considered missing.

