8.1 Screening

Participants must sign an informed consent form (ICF) prior to any study specific screening evaluations, within 28 days prior to the first dose of study treatment. The screening phase begins once written informed consent is provided and ends after 28 days or when participant receives the first dose of study treatment. Following completion of screening procedures and verifying participant eligibility based on assessments, the participant will be enrolled via the Interactive Response Technology (IRT) system. Laboratory results from the local laboratory will be used to determine participant's eligibility to the study. Refer to [Table 8-1](#) for additional details.

For laboratory evaluations used to determine eligibility, a repeated evaluation within the screening window is permitted for screening results out of the defined range. If the repeated laboratory result meets the criteria, that result may be used to determine eligibility. If the repeated laboratory result does not meet the criteria, the patient will be considered a screening failure. Participants who do not meet the criteria for participation in this study (screen failure) may be rescreened once. Each case must be discussed and agreed with Novartis on a case-by-case basis.

All required screening assessments must be repeated if they do not meet the allowed time window for screening, when the subject will be rescreened for participation in the study.

If the participant already provided the ~~archival~~ tumor tissue samples for central testing of *BRAF* V600E mutation status it is not required to submit a new sample

Procedure for re-screening is as follows:

- Site must register the patient as a screen failure in IRT
- Subject number will be different from the initial screening

Adverse events that begin or worsen after informed consent should be recorded in the Adverse Events CRF. Conditions that were already present at the time of informed consent should be recorded in Medical History CRF. CRA is to review and confirm patient's eligibility for re-screening with the site. Patients may be re-screened only once and must be enrolled within 28 days after the recorded rescreening date. All evaluations including original assessments and repeated assessments must be collected on the eCRF.

Participants will be enrolled based on a positive *BRAF* V600E mutation test performed using an NMPA/MOH-approved assay as part of study inclusion criteria ([Section 5.1](#)).

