8.3 Efficacy

8.3.1 Efficacy assessments

Tumor response will be assessed locally and by independent central review according to the Novartis guideline version 3.2 ([Section 16](#)) based on RECIST 1.1 ([Eisenhauer et al 2009](#)). The imaging assessment collection plan is presented in [Table 8-2](#). Details of the central review process will be described in the independent review charter.

Imaging data will be centrally collected and checked for quality by an imaging Contract Research Organization (CRO) designated by Novartis. The central independent review's assessment will be used for the primary endpoint analysis and local investigator's assessment will be used for treatment decision making.

Information regarding prior interventions (e.g., radiotherapy), pre-existing radiographic findings that mimic metastatic disease at baseline/screening and prior interventions should be transmitted to the imaging CRO via the Baseline Clinical Form along with the baseline images. Sites must ensure the data entered on the form is consistent with the data entered in the clinical database.

Information regarding cytology/histology results should be transmitted to the imaging CRO via the cytology and histology report form for all visits, when applicable, for review by the independent radiologist. Sites must ensure the data entered on the form is consistent with the data entered in the clinical database.

Baseline imaging assessments

Imaging assessments will be performed at screening/baseline within 28 days of start of treatment (Day -28 to Day -1 prior to Day 1).

Any imaging assessments already completed during the regular work-up of the participant within 28 days prior to start of treatment, including before signing the main study ICF, can be considered as the baseline images for this study. Any imaging assessments obtained after enrollment cannot be considered baseline images. The following assessments are required at screening/baseline:

- Chest, abdomen, and pelvis CT or MRI
- Brain CT or MRI
- Whole body bone scan
- Localized bone CT, MRI, or x-ray, for any lesions identified on the whole body bone scan that are not visible on the chest, abdomen, and pelvis CT or MRI
- Color photography including a metric ruler to measure the size of the lesion for any skin lesions present

- CT or MRI of other metastatic sites (e.g. neck), if clinically indicated

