16.1.2.5 Evaluation of overall lesion response

The evaluation of overall lesion response at each assessment is a composite of the target lesion response, non-target lesion response and presence of new lesions as shown below in [Table 16-3](#).

Table 16-3 Overall lesion response at each assessment

Target lesions	Non-target lesions	New Lesions	Overall lesion response
CR	CR	No	CR ¹
CR	Non-CR/Non-PD ³	No	PR
CR, PR, SD	UNK	No	UNK
PR	Non-PD and not UNK	No	PR ¹
SD	Non-PD and not UNK	No	SD ^{1, 2}
UNK	Non-PD or UNK	No	UNK ¹
PD	Any	Yes or No	PD
Any	PD	Yes or No	PD
Any	Any	Yes	PD

1. This overall lesion response also applies when there are no non-target lesions identified at baseline.

2. Once confirmed PR was achieved, all these assessments are considered PR.

3. As defined in [Section 16.1.2.4](#).

If there are no baseline scans available at all, then the overall lesion response at each assessment should be considered Unknown (UNK).

In some circumstances it may be difficult to distinguish residual disease from normal tissue. When the evaluation of complete response depends on this determination, it is recommended that the residual lesion be investigated (fine needle aspirate/biopsy) to confirm the CR.

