#### **2.1.1.6 Treatment periods**

The overall observation period will be divided into three mutually exclusive segments:

1. pre-treatment period: from day of patient's informed consent to the day before first dose of study medication
2. on-treatment period: from day of first dose of study medication to 30 days after last dose of study medication
3. post-treatment period: starting at day 31 after last dose of study medication.

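### The SAP ties baseline to a screening period it does not define, so pre-dose Day 1 laboratory values and vital signs can be counted as on-treatment or post-baseline

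*SAP*

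**What the plan says.** **Baseline.** SAP 2.1.1.4 gives the general rule: "Baseline will be defined as the most recent non-missing value during the screening period prior to the first dose of study treatment". The same limit is repeated for laboratory data. If nothing qualifies, the consequence is explicit: "If patients have no value as defined above, the baseline results will be considered missing". There is one exception: "For Patient Reported Outcomes (PRO), baseline date will be the same as Cycle 1 Day 1 for each participant".

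**Screening period.** The SAP uses the term without dating it. Protocol 8.1 says: "The screening phase begins once written informed consent is provided and ends after 28 days or when participant receives the first dose". Protocol Table 8-1 sets screening at Days -28 to -1 and places Day 1 in the treatment phase.

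**Treatment periods.** SAP 2.1.1.6 divides follow-up into three mutually exclusive segments. The pre-treatment segment runs from consent to the day before first dose. The next is the "on-treatment period: from day of first dose of study medication to 30 days after last dose of study medication". Day 1 is not split into before and after dosing.

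**Day 1 schedule.** Table 8-1 marks vital signs, body weight, ECOG, hematology, chemistry and urinalysis on Day 1. It marks no ECG, echocardiogram, coagulation panel or tumor imaging that day.

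**Imaging.** Protocol 8.3.1 accepts routine work-up scans from the 28 days before treatment, "including before signing the main study ICF, can be considered as the baseline images for this study".

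**The concern.** A baseline for a safety table should be the last value before drug exposure, and that value should not reappear on the treatment side of the comparison. Neither is assured here. Table 8-1 calls for laboratory tests and vital signs on Day 1, which would normally be the freshest baseline. Whether they count depends on which protocol window the programmer adopts. Whichever is chosen, the on-treatment period includes them by calendar date.

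At stake are the tables that set a baseline against a worst later value:
- the laboratory shift tables and worst post-baseline grades in SAP 2.7.3;
- the vital-sign shifts and changes from baseline in SAP 2.7.4.2;
- the percent change in weight reported in the same section.

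The study has a single arm, so no control group would show the same pre-existing abnormalities and put them in context.

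A smaller issue concerns imaging. If screening starts at consent, a scan that Protocol 8.3.1 accepts as baseline does not meet the SAP wording.

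**Working it through.** The plan gives no figure to reproduce. The check sets the windows side by side and then gauges scale.

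**Step 1: which window admits what.** The test cases are a Day 1 value taken before dosing, and a scan on Day -20 from a participant who consented on Day -10.

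| Window | Source | Day 1 pre-dose value | Pre-consent scan |
|---|---|---|---|
| Consent to 28 days or first dose | Protocol 8.1 | in | out |
| Day -28 to Day -1 | Protocol Table 8-1; 8.3.1 for imaging | out | in |
| Consent to day before first dose (called pre-treatment, not screening) | SAP 2.1.1.6 | out | out |

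Each protocol window produces one exclusion and not the other. None of the three admits both values.

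**Step 2: what happens to the Day 1 value.**
- *Table 8-1 window.* It is not baseline. Under SAP 2.1.1.3, Day -28 is 28 days before first dose, so the baseline used instead can be up to 28 days old. The Day 1 value falls after that baseline, so it can be the worst post-baseline laboratory grade or vital sign. It can also be the worst on-treatment laboratory value.
- *Protocol 8.1 window.* It is baseline. It also lies inside the on-treatment period, because that begins on the calendar day of first dose. It can therefore appear on both sides of a shift table as baseline and as worst on-treatment value.

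The laboratory shift tables are thus exposed under either window. The worst post-baseline summaries and the age of the baseline are affected only under Table 8-1.

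**Step 3: scale.** Assume a parameter unaffected by drug, one Day 1 value and k later values, all exchangeable and without ties. The chance that the Day 1 value is the worst of the k + 1 is 1/(k + 1). Visits are every 3 weeks, so k later visits reach week 3k.

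| k (assumed) | Reaches week | 1/(k + 1) |
|---|---|---|
| 1 | 3 | 1/2 = 50% |
| 5 | 15 | 1/6 = 17% |
| 10 | 30 | 1/11 = 9% |
| 17 | 51 | 1/18 = 6% |

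These are chances per participant and parameter that the Day 1 value supplies the worst value. A graded table changes less often, because the next-worst value frequently has the same grade. The distortion is largest for participants who leave treatment early.

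**Step 4: the scan.** Under the consent-based window, the Day -20 scan fails the SAP wording and the missing-baseline sentence applies. The SAP tumor item that clearly draws on a baseline value is the descriptive sum of target-lesion diameters in SAP 2.3.

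**The case against.** The strongest reply is that the text settles neither exclusion. Protocol 8.1 lets a pre-dose Day 1 value in; Table 8-1 lets a pre-consent scan in. A reader might infer that the SAP shuts out both. That requires the screening period to mean the pre-treatment period of SAP 2.1.1.6, and the SAP never equates them. This part of the reply stands: the defect is an undefined term with conflicting windows. It does not clear the laboratory shift tables, because the on-treatment period takes in all of Day 1 whichever window applies.

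Second, the documents do not say that Day 1 laboratory tests and vital signs are taken before dosing. Protocol 8.5.1 requires this of the questionnaires. This also stands. Pre-dose timing is a reasonable expectation, not a stated fact, and the remedy must not assert it.

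Third, the separate Day 1 rule for questionnaires might suggest that the authors saw Day 1 as outside screening for everything else. The inference is weak. Table 8-1 has no screening questionnaire, so those outcomes needed their own rule in any case.

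Fourth, the tables are descriptive, and a Day 1 value alters a worst-value summary only when it is the worst. That limits the size of the problem but does not remove it.

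**Conclusion.** The point holds as a defect in the baseline and period rules for descriptive safety tables. Under the Table 8-1 window, baseline for laboratory tests, vital signs and weight can be up to 28 days older than a Day 1 value already in the database, and that Day 1 value can count as post-baseline. Under either window it can be the worst on-treatment laboratory value. For a parameter that does not change, the chance of this runs from 50% to 6% as assumed later values rise from 1 to 17. The conclusion rests on at least some Day 1 values being taken before dosing.

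ECG and LVEF are not affected, since neither is scheduled on Day 1. For pre-consent scans the consequence is limited to descriptive baseline tumor data, and only under a consent-based window.

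A reader might go further and infer that such participants become unknown for response, count as non-responders under SAP 2.5.3, and are censored for PFS at treatment start. The documents do not support this. Protocol Appendix 16.1.2.5 assigns unknown response only where no baseline scan is available at all, and situation A in Table 16-5 requires that there be no baseline assessment. A scan accepted under Protocol 8.3.1 exists and is a baseline image. Best overall response for the primary endpoint comes from the central read of those images, and nothing makes SAP 2.1.1.4 an input to that read. No ORR or PFS effect should be attached to this point.

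**What to change.** Revise SAP 2.1.1.4 and add a matching sentence to 2.1.1.6:

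1. Baseline is the last non-missing value before the first dose, including Day 1 values recorded as pre-dose. The questionnaire rule stays as it is.
2. State how Day 1 values without a recorded time are handled, for example treated as pre-dose and flagged in the listings.
3. Values used as baseline, or known to be pre-dose, are excluded from on-treatment and worst post-baseline summaries.
4. Baseline imaging follows Protocol 8.3.1: within 28 days before first dose, regardless of consent date.

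The Day 1 column of Table 8-1 should not be relabelled as pre-dose after the fact. That would assert a timing for data already collected, and any sample actually drawn after dosing would be turned into baseline.

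The cost is a short SAP revision and a programming rule, with no new data. The drawback is that Day 1 values without times need an assumption. The documents do not say whether Day 1 dosing and sampling times are recorded, so the number of flagged values should be reported with the tables.

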#### **2.1.1.5 Last contact date**

Last contact date will be used for the censoring of patients in the analysis of overall survival.

The last contact date will be derived for patients not known to have died at the analysis cut-off using the last complete date among the following:

- Last contact date collected on the 'Survival information' eCRF.
- All assessment dates (e.g. tumor assessment, laboratory/PK collection dates, vital signs assessment, performance status, ECG assessment). Note, only a true on study assessment date or patient contact date will be used. If there is a visit date without evidence of any actual assessment performed that date will not be used. No dates post cut-off will be used.
- Medication dates including study medications, concomitant medications, and anti-cancer therapies administered after study treatment discontinuation.
- Adverse event dates.

Note: The cut-off date will not be used for last contact date, unless the patient was seen or contacted on that date.

#### **2.1.1.6 Treatment periods**

The overall observation period will be divided into three mutually exclusive segments:

1. pre-treatment period: from day of patient's informed consent to the day before first dose of study medication
2. on-treatment period: from day of first dose of study medication to 30 days after last dose of study medication
3. post-treatment period: starting at day 31 after last dose of study medication.

## **2.2 Analysis sets**

The Full Analysis Set (FAS) comprises all subjects who received at least one dose of study drug from enrollment up to the cut-off date. This population will be the primary population for efficacy and safety analysis.

The Pharmacokinetic Analysis Set (PAS) will consist of those subjects in the FAS for whom a pharmacokinetic sample is obtained and analyzed.

#### **2.2.1 Subgroup of interest**

Not applicable.

## **2.3 Patient disposition, demographics and other baseline characteristics**

The FAS will be used for all patient demographic and baseline characteristic summaries and listings with the exception of screen failures.

### **Basic demographic and background data**

All demographic and baseline disease characteristics data will be presented overall and listed by treatment group (previously treated and treatment naïve) and overall. Categorical data (e.g. gender, age groups: <65 and ≥ 65 years, race, ethnicity, smoking history, ECOG performance status, etc.) will be summarized by frequency count and percentages; the number and percentage of subjects with missing data will be provided. Continuous data (e.g. age, weight, height, BMI, etc.) will be summarized by descriptive statistics (mean, standard deviation, median, minimum, and maximum). BMI (kg/m^2) will be calculated as weight[kg] / (height[m]) using weight at Baseline.

### **Diagnosis and extent of cancer**

Summary statistics will be tabulated for diagnosis and extent of cancer. This analysis will include the following: primary site of cancer at initial diagnosis, diagnosis of disease, BRAF mutation status, details of tumor histology/cytology, stage at study entry per AJCC Edition 8, time since initial diagnosis, time from initial diagnosis to first recurrence/progression (in months), time since most recent relapse/progression to randomization (in months), presence/absence of target and non-target lesions, sum of lesion diameter for target lesions at baseline, number and type of metastatic sites involved. Note: Presence/absence of target and non-target lesions will be based on the data collected on RECIST target/non-target lesion assessment eCRF pages. Metastatic sites will be based on diagnosis page. Tumor (T) stage at study entry, lymph nodes (N) stage at study entry, and metastases (M) at study entry will be further listed in the Subject disease history listing.

### **Medical history**

Medical history and ongoing conditions, including cancer-related conditions and symptoms will be summarized and listed. Separate summaries will be presented for ongoing and historical medical conditions. The summaries will be presented by primary system organ class and preferred term. Medical history and current medical conditions are coded using the Medical Dictionary for Regulatory Activities (MedDRA) terminology.

### **Prior anti-cancer therapy**

Prior anti-neoplastic (anti-cancer) therapy will be listed in three separate categories: 1. medications, 2. radiotherapy, and 3. surgery.

The number and percentage of patients who received any prior anti-neoplastic medications, prior anti-neoplastic radiotherapy or prior anti-neoplastic surgery will be summarized.

Prior anti-neoplastic medications will be summarized by chemotherapy (medication) setting, other therapy (medication) setting, number of prior regimens of anticancer medications. Prior antineoplastic medications will also be summarized by ATC class, and preferred term.

## Screen failures

Screen failures are patients who have been enrolled e.g. signed IFC and have failed to meet inclusion or exclusion criteria. These patients are not treated with study drug. Frequency counts and percentages will be tabulated for all enrolled patients as follows:

- Number (%) of patients who completed screening phase (based on the presence of study phase completion date and the 'Next phase entered' is 'Treatment' in the 'Screening Phase Disposition' page);
- Number (%) of patients who discontinued during screening phase ( based on the presence of date of discontinuation and discontinuation / "subject status" reason entered and 'Will the subject continue into the next phase of the trial' is 'No' in the 'Screening Phase Disposition' page);
- Reasons for screening phase discontinuation (based on reasons recorded in Screening Phase Disposition' page).

All screen failure patients with reasons for screen failure will be listed. Violations of inclusion/exclusion criteria leading to screen failures will be summarized by criteria.

### 2.3.1 Patient disposition

The number (%) of screened and not-randomized subjects and the reasons for screening failure will also be displayed. The number (%) of subjects in the FAS who are still on treatment, who discontinued the study phases and the reason for discontinuation will be presented overall and by treatment group.

A summary of the number of subjects in FAS and PAS will be provided. A listing of subjects excluded from analysis populations will also be provided. Anyone who had a randomization ID but without a study treatment will be excluded from FAS. Anyone who do not have PK sample will be excluded from PAS.

A summary of study treatment status will be provided. This display will show the number and percentage of subjects who discontinued study treatment, has treatment ongoing or completed the study, and a summary of the primary reasons for discontinuation of study treatment or death. Reasons for study treatment discontinuation will be presented in the order they are displayed in the eCRF.

A listing of study treatment discontinuation will be generated. The listing will include last dose date, and reasons for study treatment discontinuation.

